4.2.2 Olaparib Dose Reductions

Initial Dose

300 mg twice daily

In case a dose reduction is necessary, olaparib will be administered as follows:

Table 5	Dose reductions for study treatment to manage adverse events								
Initial Dose	Following re-challenge post interruption: Dose reduction 1	Dose reduction 2							
300 mg twice daily	250 mg twice daily	200 mg twice daily							
Table 6	Dose reduction for olaparib if patient develop	s moderate renal impairment							
Initial Dose	Moderate renal impairment (cal- Cockcroft -Gault equation or ba between 31 and 50 ml/min): Dos	sed on a 24 hour urine test							
300 mg twice daily	200 mg twice daily								
Table 7	Dose reductions for study treatment if patient	t has to start taking a strong or							

Strong CYP3A inhibitor

100 mg twice daily

Any toxicity observed during the course of the study could be managed by interruption of the dose of study treatment or dose reductions. Repeat dose interruptions are allowed as required, for a maximum of 4 weeks on each occasion. If the interruption is any longer, the study team must be informed. Olaparib can be dose reduced to 250 mg twice daily as a first step and to 200 mg twice daily as a second step. If the reduced dose of 200 mg twice daily is not tolerable, no further dose reduction is allowed and Olaparib should be discontinued. Once Olaparib dose is reduced, escalation is not permitted (except following concomitant treatment with CYP3A4 inhibitors).

When Olaparib dose reduction is necessary patients will take one 150 mg tablet and one 100 mg tablet twice daily or two x 100 mg tablet twice daily, or one 150 mg tablet twice daily or one 100 mg tablet twice daily.

4.2.3 Olaparib Management of Adverse Events

Management of haematological toxicity 4.2.3.1 Management of anaemia

Moderate CYP3A inhibitor

150 mg twice daily

Table 8	Management of anaemia							
Haemoglobin	Action to be taken							
Hb < 10 but ≥ 8 g/dl	First occurrence:							
(CTCAE Grade 2)	Give appropriate supportive treatment and investigate causality.							
	Investigator judgement to continue olaparib with supportive treatment (eg transfusion) or interrupt dose for a maximum of 4 weeks. Olaparib can be restarted if Hb has recovered to > 9g/dl.							
	Subsequent occurrences:							
	If Hb< 10 but ≥ 9 g/dI investigator judgement to continue olaparib with supportive treatment (eg transfusion) or dose interrupt (for max of 4 weeks) and upon recovery dose reduction may be considered (to 250 mg twice daily as a first step and to 200 mg twice daily as a second step).							
	If Hb< 9 but \geq 8 g/dI, dose interrupt (for max of 4 weeks) until Hb \geq 9 g/dI and upon recovery dose reduction may be considered (to 250 mg twice daily as a first step and to 200 mg twice daily as a second step).							
Hb < 8 g/dl (CTCAE Grade 3)	Give appropriate supportive treatment (e.g. transfusion) and investigate causality.							
,	Interrupt Olaparib for a maximum of 4 weeks until improved to Hb ≥ 9 g/dl.							
	Upon recovery dose reduce to 250 mg twice daily as a first step and to 200 mg twice daily as a second step in the case of repeat Hb decrease.							

Common treatable causes of anaemia (e.g., iron, vitamin B12 or folate deficiencies and hypothyroidism) should be investigated and appropriately managed. In some cases management of anaemia may require blood transfusions. For cases where patients develop prolonged haematological toxicity (≥2 week interruption/delay in olaparib due to CTC grade 3 or worse anaemia and/or development of blood transfusion dependence), refer to guidance later in this section for the management of this.

Management of neutropenia, leukopenia and thrombocytopenia

Table 9 Management of neutropenia, leukopenia and thrombocytopenia

Toxicity	Study treatment dose adjustment					
CTCAE Grade 1-2	Investigator judgement to continue treatment or if dose interruption, this should be for a maximum of 4 weeks; appropriate supportive treatment and causality investigation					
CTCAE Grade 3-4	Dose interruption until recovered to CTCAE gr 1 or better for a maximum of 4 weeks. If repeat CTCAE grade 3-4 occurrence, dose reduce olaparib to 250 mg twice daily as a first step and 200 mg twice daily as a second step					

Adverse event of neutropenia and leukopenia should be managed as deemed appropriate by the investigator with close follow up and interruption of study drug if CTC grade 3 or worse neutropenia occurs.

Primary prophylaxis with Granulocyte colony-stimulating factor (G-CSF) is not recommended, however, if a patient develops febrile neutropenia, olaparib should be stopped and appropriate management including G-CSF should be given according to local hospital guidelines. Please note that G-CSF should not be used within at least 24 h (7 days for pegylated G-CSF) of the last dose of study treatment unless absolutely necessary.

Platelet transfusions, if indicated, should be done according to local hospital guidelines.

For cases where patients develop prolonged haematological toxicity (≥2 week interruption/delay in olaparib due to CTC grade 3 or worse), refer to guidance later in this section for the management of this.

Management of prolonged haematological toxicities while on study treatment

If a patient develops prolonged haematological toxicity such as:

≥2 week interruption/delay in olaparib due to CTC grade 3 or worse anaemia and/or development of blood transfusion dependence

≥2 week interruption/delay in olaparib due to CTC grade 3 or worse neutropenia (ANC < 1 x 10⁹/L)

≥2 week interruption/delay in olaparib due to CTC grade 3 or worse thrombocytopenia and/or development of platelet transfusion dependence (Platelets < 50 x 10⁹/L)

Check weekly differential blood counts including reticulocytes and peripheral blood smear. If any blood parameters remain clinically abnormal after 4 weeks of dose interruption, the patient should be referred to haematologist for further investigations. Bone marrow analysis and/or blood cytogenetic analysis should be considered at this stage according to standard haematological practice. Olaparib should be discontinued if blood counts do not recover to CTC gr 1 or better within 4 weeks of dose interruption.

Development of a confirmed myelodysplastic syndrome or other clonal blood disorder should be reported as an SAE and full reports must be provided by the investigator to Merck. Olaparib treatment should be discontinued if patient's diagnosis of MDS and/or AML is confirmed.

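### At the 4-week limit after grade 3 anaemia, haemoglobin of 9.0 to below 10 g/dl meets both Table 8's condition to resume olaparib and the prolonged-toxicity condition to discontinue it

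*Combined protocol and SAP*

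**What the plan says.** Three parts of Section 4.2.3 bear on the point.

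- **Table 8 (management of anaemia).** The row for "Hb < 10 but ≥ 8 g/dl" is labelled CTCAE grade 2, and the row below 8 g/dl is labelled grade 3. For grade 3 the instruction is "Interrupt Olaparib for a maximum of 4 weeks until improved to Hb ≥ 9 g/dl", and then "Upon recovery dose reduce to 250 mg twice daily as a first step", with a second step if haemoglobin falls again.
- **Text under Table 8.** For prolonged toxicity, which for anaemia means "≥2 week interruption/delay in olaparib due to CTC grade 3 or worse anaemia and/or development of blood transfusion dependence", the reader is told to "refer to guidance later in this section for the management of this".
- **Paragraph on prolonged haematological toxicities.** It repeats that trigger and asks for weekly counts. It calls for referral to a haematologist if any parameter is still clinically abnormal after 4 weeks off drug. It closes with "Olaparib should be discontinued if blood counts do not recover to CTC gr 1 or better within 4 weeks of dose interruption".

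Section 4.2.2 repeats the 4-week maximum and the dose steps, and Section 7.2 repeats the dose steps. Neither gives a haemoglobin threshold for restarting.

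**The concern.** Two operative instructions use different definitions of recovery for the same event. Table 8 uses a haemoglobin value that the same table places in grade 2. The prolonged-toxicity paragraph uses grade 1 or better. Where both apply, a site cannot tell whether olaparib resumes at a reduced dose or stops for good.

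This matters first for patient safety. It also affects which regimen a patient is receiving when response and clinical benefit are assessed, since olaparib is one of only two study drugs. Section 10.7 requires the study to be run exactly as the approved protocol describes, and in the overlapping case following one instruction departs from the other. Section 4.8 also treats patients who do not complete 6 weeks of both drugs as not evaluable for efficacy and replaces them, so a stop early in treatment could affect who is counted. Section 1.1 describes the dose-limiting toxicities of PARP inhibition as mainly haematologic, so the situation is foreseeable, although its frequency is not stated.

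**Working it through.** The plan states no figure to reproduce. The check compares haemoglobin ranges and time windows.

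**Step 1: what grade 1 means here.** Table 8 puts 8 to below 10 g/dl in grade 2. By that boundary, grade 1 or better is 10 g/dl or more. This is inferred from Table 8's labels, since the table has no grade 1 row.

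**Step 2: the two rules side by side, after grade 3 anaemia (below 8 g/dl).**

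| | Table 8, grade 3 row | Prolonged-toxicity paragraph |
|---|---|---|
| Applies from | start of interruption | 2 weeks of interruption, and/or transfusion dependence |
| Time limit | 4 weeks | 4 weeks |
| Recovery means | 9 g/dl or more | grade 1 or better, i.e. 10 g/dl or more |
| Consequence | resume at reduced dose if met | discontinue if not met |

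**Step 3: the haemoglobin overlap.** Values that satisfy Table 8 but not the later paragraph run from 9.0 up to, but not including, 10.0 g/dl. The band is 10 − 9 = 1 g/dl wide, and all of it is grade 2.

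**Step 4: the timing.**

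- *Under 2 weeks, no transfusion dependence.* Only Table 8 applies, so there is no conflict.
- *Weeks 2 to 4.* Both texts are in play. A patient at 9.5 g/dl in week 3 meets Table 8's condition to resume. The discontinuation condition is not yet met, because failure to recover within 4 weeks cannot be established in week 3. What is left open is whether that patient, once restarted, must still reach grade 1 by week 4 or whether the restart closes the matter.
- *At the 4-week limit.* A patient at 9.5 g/dl has reached Table 8's target within its permitted time and should resume at a reduced dose. The same patient is still grade 2, has not reached grade 1 within 4 weeks, and should be discontinued. The instructions are opposite.

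**Step 5: who is in the definite case.** Under Table 8 alone, a patient reaching 9 g/dl earlier could already have resumed. The outright contradiction therefore falls on a patient whose haemoglobin first reaches the band at about the week-4 check, or who was kept off drug in the band until then.

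**Step 6: comparison with Table 9.** For grade 3 to 4 neutropenia, leukopenia and thrombocytopenia, Table 9 interrupts for up to 4 weeks until grade 1 or better. That matches the prolonged-toxicity paragraph, so the mismatch is confined to the anaemia table.

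**The case against.** The best answer is the cross-reference. The text directly under Table 8 sends patients with a prolonged interruption to the later guidance, and an ordinary reader may take Table 8 to govern short interruptions and the specific rule to govern from week 2. On that reading the protocol already sets an order of precedence. This has real force and narrows the point. It does not remove it: the cross-reference says where to look, not that the Table 8 criterion lapses, and Table 8 states its 9 g/dl target for the full 4 weeks. If precedence was intended, Table 8 misdirects a reader from week 2 onward and still needs a qualifying phrase.

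Four stronger readings are tempting and are not supported:

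- A reader might infer that everyone interrupted for 2 to 4 weeks with haemoglobin in the band receives opposite instructions. The later paragraph gives until week 4 to recover and sets no restart threshold of its own, so before then there is ambiguity rather than contradiction.
- A reader might treat discontinuation as mandatory. The paragraph says should.
- A reader might add Table 8's line "Olaparib can be restarted if Hb has recovered to > 9g/dl" as further evidence. It belongs to the first-occurrence part of the grade 2 row. Grade 2 anaemia does not meet the grade 3 interruption trigger, so the line does not bear on this conflict.
- A reader might note that one patient is 1/20 = 5% of the planned sample and take that as the effect. It is only the weight of one patient. The documents give no rate of grade 3 anaemia for this combination, and no route to a changed response result is shown.

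**Conclusion.** The inconsistency is real and narrow. It is definite for a patient with an interruption for grade 3 or worse anaemia whose haemoglobin is 9.0 to below 10 g/dl at the 4-week limit. It is an ambiguity for a patient restarted in that band between weeks 2 and 4. There is no conflict for shorter interruptions without transfusion dependence.

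The conclusion rests on two readings: that grade 1 or better means at least 10 g/dl, taken from Table 8's own labels, and that the blood counts in the later paragraph include haemoglobin, which follows from anaemia being the first trigger listed there. The number of patients affected cannot be derived from the documents, and nothing here shows that the trial's efficacy conclusion would change. The case for acting is that sites need one instruction on a safety decision and that supplying it is cheap.

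**What to change.** Reconcile Table 8 and the prolonged-toxicity paragraph in Section 4.2.3. The revised text should state:

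1. which recovery criterion and which time limit apply once an interruption for grade 3 or worse anaemia reaches 2 weeks;
2. whether a patient restarted between weeks 2 and 4 must still meet a further criterion by week 4;
3. in the cross-reference under Table 8, whether the later guidance replaces the table's threshold or adds to it.

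The choice of threshold is a clinical decision for the sponsor and investigators, and this review does not propose one. The cost is a few lines at the next amendment, with the IRB approval that Section 10.8 requires before implementation. The sample size, stopping rule and analyses are unaffected.

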4.2.3.2 Management of non-haematological toxicity

Repeat dose interruptions are allowed as required, for a maximum of 4 weeks on each occasion. If the interruption is any longer than this the study monitor must be informed. Where toxicity reoccurs following re-challenge with olaparib, and where further dose interruptions are considered inadequate for management of toxicity, then the patient should be considered for dose reduction or must permanently discontinue olaparib.

Olaparib can be dose reduced to 250 mg twice daily as a first step and to 200 mg twice daily as a second step. Treatment must be interrupted if any NCI-CTCAE grade 3 or 4 adverse event occurs which the investigator considers to be related to administration of study treatment.

Management of new or worsening pulmonary symptom

If new or worsening pulmonary symptoms (e.g., dyspnoea) or radiological abnormalities occur in the absence of a clear diagnosis, an interruption in study treatment dosing is recommended and further diagnostic workup (including a high resolution CT scan) should be performed to exclude pneumonitis.

Following investigation, if no evidence of abnormality is observed on CT imaging and symptoms resolve, then study treatment can be restarted, if deemed appropriate by the investigator. If significant pulmonary abnormalities are identified, these need to be discussed with the Study Physician.

Management of nausea and vomiting

Events of nausea and vomiting are known to be associated with olaparib treatment. These events are generally mild to moderate (CTCAE grade 1 or 2) severity, intermittent and manageable on continued treatment. The first onset generally occurs in the first month of treatment for nausea and within the first 6 months of treatment for vomiting. For nausea, the incidence generally plateaus at around 9 months, and for vomiting at around 6 to 7 months.

No routine prophylactic anti-emetic treatment is required at the start of study treatment, however, patients should receive appropriate anti-emetic treatment at the first onset of nausea or vomiting and as required thereafter, in accordance with local treatment practice guidelines. Alternatively, olaparib tablets can be taken with a light meal/snack (ie 2 pieces of toast or a couple of biscuits). As per international guidance on anti-emetic use in cancer patients (ESMO, NCCN), generally a single agent antiemetic should be considered eg dopamine receptor antagonist, antihistamines or dexamethasone.

Interruptions for intercurrent non-toxicity related events

Olaparib dose interruption for conditions other than toxicity resolution should be kept as short as possible.

All dose reductions and interruptions (including any missed doses), and the reasons for the reductions/interruptions are to be recorded in the eCRF.

Olaparib should be stopped at least 3 days prior to planned surgery. After surgery study treatment can be restarted when the wound has healed. No stoppage of study treatment is required for any needle biopsy procedure.

Study treatment should be discontinued for a minimum of 3 days before a patient undergoes radiation treatment. Study treatment should be restarted within 4 weeks as long as any bone marrow toxicity has recovered.

Because the AEs related to olaparib may include asthenia, fatigue and dizziness, patients should be advised to use caution while driving or using machinery if these symptoms occur.

Table 10 Dose reductions for study treatment

Initial Dose	Following re-challenge post interruption: Dose reduction 1	Dose reduction 2
300 mg twice daily	250 mg twice daily	200 mg twice daily

4.2.3.3 Renal impairment

If subsequent to study entry and while still on study therapy, a patient's estimated CrCl falls below the threshold for study inclusion (≥51 ml/min), retesting should be performed promptly. A dose reduction is recommended for patients who develop moderate renal impairment (calculated creatinine clearance by Cockcroft-Gault equation or based on a 24 hour urine test of between 31 and 50 ml/min) for any reason during the course of the study: the dose of olaparib should be reduced to 200 mg twice daily.

Because the CrCl determination is only an estimate of renal function, in instances where the CrCl falls to between 31 and 50 mL/min, the investigator should use his or her discretion in determining whether a dose change or discontinuation of Olaparib therapy is warranted.

Olaparib has not been studied in patients with severe renal impairment (creatinine clearance ≤ 30 ml/min) or end-stage renal disease; if patients develop severe impairment or end stage disease is it recommended that olaparib be discontinued.

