3.0 PATIENT ELIGIBILITY

3.1 Inclusion Criteria

- 3.1.1 Be willing and able to provide written informed consent/assent for the trial
- **3.1.2** Be ≥18 years of age on day of signing informed consent
- 3.1.3 Advanced BRCA-mutated and/or HDR-defect breast cancer progressing on or after prior therapy for metastatic disease or locally advanced disease; Prior therapy is defined as follows: for triple negative breast cancer progressing after at least 1 line of any prior chemotherapy; for HER2 positive disease must have progressed after at least two HER2 directed therapies in the metastatic setting including ado-trastuzumab emtansine (T-DM1); for hormone receptor positive disease (ER, PR, or both) must have progressed after a CDK4/CDK6 inhibitor plus hormonal therapy. Patients with progression within 12 months from previous neoadjuvant or adjuvant treatment could be enrolled in the study as 1st line therapy in metastatic setting.
- 3.1.4 Measurable disease by RECIST 1.1, with at least one lesion, not previously irradiated, that can be accurately measured at baseline as ≥ 10 mm in the longest diameter (except lymph nodes which must have short axis ≥ 15 mm) with computed tomography (CT) or magnetic resonance imaging (MRI) and which is suitable for accurate repeated measurements. Patients with non-measurable bone metastases in addition to measurable disease are eligible; however patients with non-measurable bone disease as the only site(s) of disease are not eligible.
- **3.1.5** ECOG 0 or 1
- **3.1.6** Documented BRCA deleterious germline or somatic mutation *AND/OR* HDR-defect.
- **3.1.7** FFPE tumor tissue available for analysis
- **3.1.8** Adequate organ function as defined in Table 1

Table 1 Adequate Organ Function Laboratory Values

System	Laboratory Value		
Hematological			
Absolute neutrophil count (ANC)	$\geq 1500/\mu L$		
Platelets	$\geq 100~000/\mu L$		
Hemoglobin	$\geq 10.0 \text{ g/dL or} \geq 5.6 \text{ mmol/L}^a$, with no blood		
	transfusion in the past 28 days		
Renal			
Creatinine OR	≤1.5 × ULN OR		
Measured or calculated ^b creatinine clearance	≥51 mL/min for participant with creatinine		
(GFR can also be used in place of creatinine or	levels >1.5 × institutional ULN		
CrCl)			
Hepatic			
Total bilirubin	≤1.5 ×ULN OR direct bilirubin ≤ULN for		
	participants with total bilirubin levels		
	>1.5 × ULN		

AST (SGOT) and ALT (SGPT)	≤2.5 × ULN (≤5 × ULN for participants with liver metastases)
Coagulation	

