International normalized ratio (INR) OR prothrombin time (PT) Activated partial thromboplastin time (aPTT)	≤1.5 × ULN unless participant is receiving anticoagulant therapy as long as PT or aPTT is within therapeutic range of intended use of anticoagulants

ALT (SGPT)=alanine aminotransferase (serum glutamic pyruvic transaminase); AST (SGOT)=aspartate aminotransferase (serum glutamic oxaloacetic transaminase); GFR=glomerular filtration rate; ULN=upper limit of normal.

Note: This table includes eligibility-defining laboratory value requirements for treatment; laboratory value requirements should be adapted according to local regulations and guidelines for the administration of specific chemotherapies.

- **3.1.9** Female subjects: Postmenopausal or evidence of non-childbearing status for women of childbearing potential: negative urine or serum pregnancy test within 28 days of study treatment and confirmed prior to treatment on day 1.

 Postmenopausal is defined as:
 - Amenorrheic for 1 year or more following cessation of exogenous hormonal treatments Luteinizing hormone (LH) and Follicle stimulating hormone (FSH) levels in the post menopausal range for women under 50
 - radiation-induced oophorectomy with last menses >1 year ago
 - chemotherapy-induced menopause with >1 year interval since last menses
 - surgical sterilisation (bilateral oophorectomy or hysterectomy)

^a Criteria must be met without erythropoietin dependency and without packed red blood cell (pRBC) transfusion within last 2 weeks.

b Creatinine clearance (CrCl) should be calculated using Cockcroft-Gault equation or based on 24-hour urine.

Estimated creatinine clearance = (140-age [years]) x weight (kg) (x F)^a

serum creatinine (mg/dL) x 72

^a where F=0.85 for females and F=1 for males.

- 3.1.10 Women of childbearing potential and their partners, who are sexually active, must agree to the use of TWO highly effective forms of contraception in combination (as described in Appendix). This should be started from the signing of the informed consent and continue throughout the period of taking study treatment and for at least 1 month after last dose of study drug(s), or they must totally/truly abstain from any form of sexual intercourse (as described in Appendix).

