4.0 TREATMENT PLAN

4.1 Treatment Dosage and Administration

This is an open-label, single-arm pilot study in 20 subjects with advanced BRCA mutation or HDR-defect associated breast cancer having progressed through standard first line therapy.

The study participation is up to 35 administrations of pembrolizumab (approximately two years).

Pembrolizumab and olaparib will be supplied by Merck.

Pembrolizumab will be administered at a dose of 200mg as a 30 minute IV infusion Q3W. Effort should be made to target infusion timing to be as close to 30 minutes as possible. However, given the variability of infusion pumps, a window of -5 minutes and +10 minutes is permitted (i.e., infusion time is 30 minutes: -5 min/+10 min).

Olaparib 300mg will be self-administered orally twice daily. The dose of olaparib used in this study is 300 mg twice daily which is the currently approved dose. Subjects will complete a compliance diary throughout the study treatment period. Olaparib tablets should be taken at the same time each day, approximately 12 hours apart with one glass of water. The tablets should be swallowed whole and not chewed, crushed, dissolved or divided. Olaparib tablets can be taken with or without food. Each container will be labelled in accordance with Good Manufacturing Practice (GMP) Annex 13 and per country regulatory requirement. If vomiting occurs shortly after the olaparib tablets are swallowed, the dose should only be replaced if all of the intact tablets can be seen and counted. Should any patient enrolled on the study miss a scheduled dose for whatever reason (e.g., as a result of forgetting to take the tablets or vomiting), the patient will be allowed to take the scheduled dose up to a maximum of 2 hours after that scheduled dose time. If greater than 2 hours after the scheduled dose time, the missed dose is not to be taken and the patient should take their allotted dose at the next scheduled time.

The Pharmacy Manual contains specific instructions for pembrolizumab dose calculation, reconstitution, preparation of the infusion fluid, and administration.

Table 2. Trial Intervention

Drug Dose/Potency	Dose/	Route of	Regimen/ Treatment
-------------------	-------	----------	--------------------

		Frequency	Administration	Period
Pembrolizumab	200 mg	Q3W	IV infusion	Day 1 of each cycle
Olaparib	300mg	BID	PO	Continuous; dispensed
				each cycle day 1 (each
				cycle=3 weeks)

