5.8 Laboratory Safety Evaluations

Details regarding specific laboratory procedures/assessments to be performed in this trial are provided in the table below.

Laboratory tests for screening should be performed within 10 days prior to the first dose of pembrolizumab. After Cycle 1, pre-dose laboratory procedures can be conducted up to 72 hours prior to dosing. Results must be reviewed by the investigator or qualified designee and found to be acceptable prior to each dose of trial treatment.

Hematology	Chemistry	Other
Hemoglobin	Albumin	Triiodothyronine (T3)
Platelets	Alkaline phosphatase	Free thyroxine (FT4)
WBC (total and differential)	Alanine aminotransferase	Thyroid stimulating hormone

	(ALT)	(TSH)
Absolute Neutrophil Count	Aspartate aminotransferase (AST)	Coagulation: PT, INR, aPTT
Absolute Lymphocyte Count	Creatinine or calculated creatinine clearance (CrCl)	
	Calcium	
	Glucose	
	Potassium	
	Sodium	
	Total Bilirubin	
	Blood Urea Nitrogen	

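### The creatinine clearance floor of 51 mL/min that Section 4.2.3.3 treats as an entry requirement is not required by Table 1 for most patients, so patients below it can start olaparib at 300 mg twice daily

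*Combined protocol and SAP*

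**What the plan says.** **Entry.** The renal row of Table 1 (Section 3.1, criterion 3.1.8) offers two alternatives joined by OR. The first is serum creatinine no higher than 1.5 × ULN. The second is a clearance of "≥51 mL/min for participant with creatinine" "levels >1.5 × institutional ULN". A footnote gives the method: "Creatinine clearance (CrCl) should be calculated using Cockcroft-Gault equation or based on 24-hour urine". No other inclusion or exclusion criterion sets a renal limit. The chemistry panel in Section 5.8 asks for creatinine or calculated CrCl, not both.

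**Dose.** Section 4.1 has one starting dose: "The dose of olaparib used in this study is 300 mg twice daily which is the currently approved dose". Tables 2, 5 and 6 agree with it.

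**On study.** Section 4.2.3.3 applies after study entry. It says that if the estimated CrCl "falls below the threshold for study inclusion (≥51 ml/min), retesting should be performed promptly". It continues: "A dose reduction is recommended for patients who develop moderate renal impairment", defined as CrCl 31 to 50 mL/min, with 200 mg twice daily as the reduced dose. For CrCl of 30 mL/min or less it states "Olaparib has not been studied in patients with severe renal impairment" and recommends stopping olaparib.

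**The concern.** Section 4.2.3.3 reads as if every patient had entered with CrCl of at least 51 mL/min. Table 1 does not ensure this, because serum creatinine alone is enough to qualify. Creatinine is a weak guide to clearance in older or lighter patients, who can have a low CrCl at an unremarkable creatinine.

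Such a patient falls between the rules. Table 1 admits her and Section 4.1 starts her at 300 mg twice daily. The reduction to 200 mg is worded for impairment that develops on study, and hers was present at entry. Since Section 5.8 lets the site report creatinine alone, her CrCl may never be calculated.

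The stake is patient safety: full-dose olaparib at a renal function where the protocol itself recommends a lower dose or, at the extreme, none. A missing baseline CrCl also makes it harder to judge on study whether clearance has fallen. That matters because Section 4.3.2 lists serum creatinine among the substrates whose exposure olaparib may raise, on limited in vitro data.

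**Working it through.** The plan states no figure to reproduce here. The check is whether a patient who meets Table 1 can have CrCl below 51 mL/min.

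**Inputs from the protocol**
- Cockcroft-Gault (Table 1 footnote): CrCl = (140 − age) × weight × F / (72 × creatinine), with F = 0.85 for women and 1 for men.
- Entry limit: creatinine ≤ 1.5 × ULN (Table 1).
- Bands: 51 mL/min or more (Table 1 and Section 4.2.3.3); 31–50 mL/min, 200 mg twice daily; 30 mL/min or less, stop (Section 4.2.3.3).

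**Assumptions**
- The institutional ULN is not given. I take 1.0 mg/dL, with a range of 0.8 to 1.2.
- Ages and weights are illustrative.

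**Step 1. CrCl in women at creatinine 1.0 mg/dL**
- 75 y, 50 kg: 65 × 50 × 0.85 / 72 = 38.4
- 70 y, 55 kg: 70 × 55 × 0.85 / 72 = 45.5
- 60 y, 60 kg: 80 × 60 × 0.85 / 72 = 56.7
- 50 y, 70 kg: 90 × 70 × 0.85 / 72 = 74.4

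Creatinine of 1.0 mg/dL meets Table 1 whenever ULN ≥ 1.0 / 1.5 = 0.67 mg/dL. The first two women are then eligible with CrCl below 51.

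**Step 2. Creatinine at which CrCl equals 51.** Divide the Step 1 values by 51.

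**Step 3. CrCl at the Table 1 limit.** Divide the Step 1 values by 1.5 × ULN, which is 1.2, 1.5 or 1.8 mg/dL.

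| Woman | Creatinine giving CrCl 51 (mg/dL) | CrCl at limit, ULN 0.8 | ULN 1.0 | ULN 1.2 |
|---|---|---|---|---|
| 75 y, 50 kg | 0.75 | 32.0 | 25.6 | 21.3 |
| 70 y, 55 kg | 0.89 | 37.9 | 30.3 | 25.3 |
| 60 y, 60 kg | 1.11 | 47.2 | 37.8 | 31.5 |
| 50 y, 70 kg | 1.46 | 62.0 | 49.6 | 41.3 |

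At ULN 1.0 all four women can be eligible with CrCl below 51, and the first can be in the band where the protocol recommends stopping. At ULN 0.8 the 50-year-old stays above 51 and none of the four reaches 30 or less.

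**Step 4. A larger man.** At 70 y and 80 kg, creatinine 1.0 gives 70 × 80 / 72 = 77.8. At the limit this becomes 51.9 for ULN 1.0 (77.8 / 1.5) and 43.2 for ULN 1.2 (77.8 / 1.8). The gap therefore mainly concerns older or lighter women.

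**Step 5. Which rule applies to an eligible woman with CrCl 38.4?** Table 1: eligible on creatinine. Section 4.1: 300 mg twice daily. Section 4.2.3.3: written for a fall, or for impairment that arises, after entry. No protocol rule sets her starting dose by renal function.

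**The case against.** The strongest reply is that several provisions could catch such a patient.

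- **Package insert.** Sections 1.2.2, 4.5 and 7.2 refer to it, and Section 4.5 says olaparib is given in accordance with it. Its renal dosing is not in the documents, and Section 4.5 concerns duration of therapy. Sections 4.1 and 4.2.2 state the initial dose without a renal exception.
- **Note under Table 1.** Laboratory requirements are to be adapted to local rules and guidelines for specific chemotherapies. The note names no renal value, and whether it covers olaparib is arguable.
- **Investigator judgement.** Section 5.8 requires acceptable results before each dose, and criterion 3.2.25 allows exclusion for a laboratory abnormality. Neither gives a renal threshold, and neither requires CrCl to be calculated.
- **Discretion at CrCl 31–50.** Section 4.2.3.3 notes that CrCl is only an estimate and leaves the choice of dose change or discontinuation to the investigator. Continuing 300 mg is thus possible on study as well. This narrows the contrast between entry and on-study handling, though the stated recommendation remains 200 mg.
- **Loose wording.** Section 4.2.3.3 may simply borrow the one CrCl figure in Table 1 as a retest trigger. Even so, the entry floor and the starting dose stay unstated.
- **The extreme is rare.** CrCl of 30 or less requires an older, light patient with creatinine near the upper limit who also has ECOG 0 or 1. That is fair: it is an illustrative extreme, and the 31–50 range is the realistic case.

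These points reduce the likely harm. None supplies a CrCl floor at entry or a renal starting dose.

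**Conclusion.** The concern holds. Section 4.2.3.3 cites an inclusion threshold that Table 1 imposes only when creatinine exceeds 1.5 × ULN. As the protocol text stands, a patient with CrCl below 51 mL/min can be eligible and start at the full dose. This does not need an unusual creatinine: 0.75 to 1.11 mg/dL is enough to bring the three lighter or older female profiles down to 51, and any higher value takes them below it.

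The weights and ages, and the ULN used for the limiting values, are assumptions. The number of such patients among 20 cannot be derived from the documents. The issue is minor for the trial as a whole: it concerns safety and consistency between sections and leaves the response endpoint and the two-stage design untouched.

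**What to change.** In the renal row of Table 1, require CrCl of at least 51 mL/min, by Cockcroft-Gault or 24-hour urine, for every entrant. Align the Section 5.8 panel so that CrCl is recorded at screening. Section 4.2.3.3 is then correct as it stands.

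If the sponsor prefers to admit patients with CrCl 31–50 mL/min, Table 1 should exclude CrCl of 30 or less, Section 4.1 should give a starting dose of 200 mg twice daily for the 31–50 group, and the reference to an inclusion threshold in Section 4.2.3.3 should be corrected.

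The cost of the main fix is one table row, a matching edit to Section 5.8, and the IRB approval that Section 10.8 requires for an amendment. Age, weight and creatinine are already obtained at screening (Sections 5.4, 5.6 and 5.8), so no new test is needed. A few otherwise eligible patients may be excluded.
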